2.5. Sequence of Planned Analyses

2.5.1. Interim Analyses

No interim analysis is planned for this study.

2.5.2. Final Analyses and Reporting

All final, planned analyses identified in this SAP will be performed after the database lock. The study will not be unblinded until the study database lock.

3. POPULATIONS / ANALYSIS SETS

3.1. Intent-to-Treat Population

The intent-to-treat (ITT) population will include all randomized patients. In this population, treatment will be assigned based on the treatment to which patients are randomized, regardless of which treatment they actually received.

3.2. Safety Population

The safety population will include all patients who receive at least 1 dose of study drug. In this population, treatment will be assigned based upon the treatment patients actually receive, regardless of the treatment to which they are randomized. All safety analysis will be based on the safety population.

3.3. Full Analysis Set

The full analysis set (FAS) will include all patients in the ITT population who receive at least 1 dose of study drug and have at least 10 days of post baseline efficacy assessments on the primary endpoint. The FAS will be used for all efficacy analysis.

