2. STUDY DESIGN

2.1. General Design and Study Schema

This is a 16-week, multicenter, randomized, double-blind, placebo-controlled, parallel-group study to compare the safety, tolerability, and efficacy of 2 dose regimens of sc TEV-48125 and placebo in adults with CM. The study consists of a screening visit, a 28-day run-in period, and a 12-week (84-day) treatment period, including a final evaluation at week 12 (end-of-treatment [EOT] visit, approximately 4 weeks [28 days] after the final dose of study drug).

This study will include female and male patients, aged 18 to 70 years, inclusive, with a history of migraine for at least 12 months and CM (as defined by International Classification of Headache Disorders, 3rd edition [ICHD-3] criteria [[Classification Committee of the IHS, 2013](#)]). The diagnosis will be prospectively confirmed via a review of headache data recorded daily during a 28-day run-in period in an electronic headache diary device.

Patients using no more than 1 preventive medication at the time of study enrollment will be allowed to remain on the medication if the medication has at least moderate evidence of efficacy for migraine ([Silberstein et al 2012](#)). Patients should not initiate any preventive migraine medications (presented in protocol Appendix B) at the time of the screening visit, and will not be allowed to initiate these medications after study start. A small subgroup of patients (approximately 30%) will be allowed to use concomitant migraine preventive medications (presented in protocol Appendix A), and no changes in these medications will be allowed until the last study assessments are complete. Patients will be allowed to use acute medications to treat acute migraine attacks, as needed.

After completing the informed consent process (screening visit [visit 1]), patients will be screened for eligibility. Eligible patients will enter a 28-day run-in period. Headache information will be captured daily throughout study participation using the electronic headache diary device. After completing the run-in period, patients will be asked to return to the study center on day 0 (visit 2). Patients who have confirmed CM and meet all other eligibility criteria (including electronic headache diary compliance criteria during the 28-day run-in period) will be randomly assigned in a 1:1:1 ratio to 1 of 3 treatment groups:

- sc administration of 675 mg of TEV-48125 at visit 2 followed by monthly sc TEV-48125 at 225 mg

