2.3. Sample Size and Power Considerations

In a Phase 2b study in CM patients, a treatment difference of 1.7 days of monthly average headache days of at least moderate severity between the TEV-48125 675/225/225 mg and placebo treatment groups was observed. A sample size of 867 patients (i.e., 289 evaluable patients completing the study per treatment group) results in at least 90% power for the study to succeed (assuming a common standard deviation [SD] of 6.29 days) at an alpha level of 0.05. Assuming a 15% discontinuation rate, 340 patients per treatment group will be randomized.

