4.4. Multiple Comparisons and Multiplicity

A fixed-sequence (hierarchical) testing procedure will be implemented to control the type 1 error rate at 0.05. The sequence of comparisons will be as follows:

1. mean change from baseline (28-day run-in period) in the monthly average number of headache days of at least moderate severity during the 12-week period after the 1st dose of study drug for the TEV 48125 675/225/225 mg treatment group versus the placebo treatment group
2. mean change from baseline (28-day run-in period) in the monthly average number of migraine days during the 12-week period after the 1st dose of study drug for the TEV 48125 675/225/225 mg treatment group versus the placebo treatment group
3. mean change from baseline (28-day run-in period) in the number of headache days of at least moderate severity during the 4-week period after the 1st dose of study drug for the TEV 48125 675/225/225 mg and TEV 48125 675 mg/placebo/placebo treatment group versus the placebo treatment group
4. proportion of patients reaching at least 50% reduction in the monthly average number of headache days of at least moderate severity during the 12-week period after the 1st dose of study drug for the TEV 48125 675/225/225 mg treatment group versus the placebo treatment group
5. mean change from baseline (28-day run-in period) in the monthly average number of headache days of at least moderate severity during the 12-week period after the 1st dose of study drug for the TEV 48125 675 mg/placebo/placebo treatment group versus the placebo treatment group
6. mean change from baseline (28-day run-in period) in the monthly average number of days of use of any acute headache medications during the 12-week period after the 1st dose of study drug for the TEV 48125 675/225/225 mg treatment group versus the placebo treatment group

7. proportion of patients reaching at least 50% reduction in the monthly average number of headache days of at least moderate severity during the 12-week period after the 1st dose of study drug for the TEV 48125 675 mg/placebo/placebo treatment group versus the placebo treatment group
8. mean change from baseline (28-day run-in period) in the monthly average number of days of use of any acute headache medications during the 12-week period after the 1st dose of study drug for the TEV 48125 675 mg/placebo/placebo treatment group versus the placebo treatment group

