9. mean change from baseline (28-day run-in period) in the monthly average number of migraine days during the 12-week period after the 1st dose of study drug for the TEV 48125 675 mg/placebo/placebo treatment group versus the placebo treatment group
10. mean change from baseline (28-day run-in period) in the monthly average number of headache days of at least moderate severity during the 12-week period after the 1st dose of study drug for the TEV 48125 675/225/225 mg treatment group versus the placebo treatment group in patients not receiving concomitant migraine preventive medications
11. mean change from baseline (28-day run-in period) in the monthly average number of headache days of at least moderate severity during the 12-week period after the 1st dose of study drug for the TEV 48125 675 mg/placebo/placebo treatment group versus the placebo treatment group in patients not receiving concomitant migraine preventive medications
12. mean change from baseline (day 0) in disability score, as measured by the HIT-6 at 4 weeks after administration of the last (3rd) dose of study drug for the TEV 48125 675/225/225 mg treatment group versus the placebo treatment group
13. mean change from baseline (day 0) in disability score, as measured by the HIT-6 at 4 weeks after administration of the last (3rd) dose of study drug for the TEV 48125 675 mg/placebo/placebo treatment group versus the placebo treatment group

If the resulting 2-sided p-value from the first comparison is ≤ 0.05 , then the next comparison of interest will be interpreted inferentially at the alpha level of 0.05. This process will continue either until all comparisons of interest are interpreted inferentially or until the point at which the resulting 2-sided p value for a comparison of interest is >0.05 . At the point where $p > 0.05$, no further comparisons will be interpreted inferentially.

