5.2. Patient Disposition

Patients screened, screening failures, and the reasons the patients were not randomized will be summarized only for the overall group using patient counts.

Patients randomized, patients randomized but not treated, patients in the safety population, ITT population, FAS and per-protocol analysis set, patients who complete the study, and patients who withdraw from the study will be summarized using descriptive statistics. Patients who withdraw from the study will also be summarized using descriptive statistics by reason for withdrawal. The denominator for calculating the percentages will be the number of ITT population.

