$$\frac{\sum \text{Days or hours of efficacy variable during the run – in period}}{\sum \text{Days with assessments recorded in the eDiary for the run – in period}} \times 28 \quad (3)$$

The *percentage of reduction* in the monthly average number of an efficacy variable will be calculated as

$$\frac{\text{baseline value} - \text{postbaseline value}}{\text{baseline value}} \times 100\% \quad (4)$$

where the baseline value is calculated by formula (3) and the postbaseline value in the equation is calculated by formula (1) for the variables *during the 12-week period* or by formula (2) for the variables *during the 4-week period* after each dose for months 1, 2 and 3.

The *baseline values* for calculating the change from baseline of the weekly number of days of the efficacy variables will use all data collected in the run-in period and be calculated as

$$\frac{\sum \text{Days of efficacy variable during the run-in period}}{\sum \text{Days with assessments recorded in the eDiary for the run-in period}} \times 7 \quad (5)$$

The *weekly number of days* of efficacy variables (e.g., days of headache with at least moderate severity, migraine days) for each week during the 4-week period after the 1st dose of study drug will be derived and normalized to 7 days equivalent using the following formula.

$$\frac{\sum \text{Days or hours of efficacy variable during the 7 days period}}{\sum \text{Days with assessments recorded in the eDiary for the 7 days period}} \times 7 \quad (6)$$

The FAS will be used for all efficacy analyses. Summaries will be presented by treatment group as randomized, unless otherwise noted. Descriptive statistics for all efficacy data will be presented by month (or week) and over 12-week period.

The primary and secondary endpoints analysis listed in Section 4.4 will be repeated for the per-protocol analysis set.

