6.3.1. Variable Definition

6.3.1.1. Electronic Headache Diary Data

The change from baseline in the monthly average number of days of secondary efficacy variables (e.g., migraine days, days with at least moderate severity, days of use of any acute headache medications etc.) *during the 12-week period* after the 1st dose of study drug will be derived similar to the primary variables using the e-diary data collected through the corresponding headache diary questions ([Appendix A](#)). The baseline values and the postbaseline values will be calculated using formula (3) and (1) respectively. *The change* is calculated as *postbaseline value – baseline value*.

The percent reduction in the monthly average number of headache days of at least moderate severity *during the 12-week period* after the 1st dose of study drug will be calculated by formula (4) in Section 6.1. The patient is considered as a responder if the percent reduction is 50% or more. If a patient is early discontinued from the study, he/she will be counted as a non-responder.

The change from baseline (run-in period) in the number of headache days of at least moderate severity *during the 4-week period* after the 1st dose of study drug will be derived similar to the primary endpoint using only the 1st month diary data. Since the patients randomized to both active treatment arms receive the same dose of TEV-48125 675-mg at their 1st dosing, their data will be combined for analyzing the endpoints *during the 4-week period* after the 1st dose of study drug.

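### The 10-diary-day full analysis set drops the earliest treated dropouts from the responder tests at steps 4 and 7, although their non-response needs no diary data (minor, avoidable exclusion)

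*SAP*

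**What the plan says.** **Analysis set.** SAP Section 3.3 requires at least one dose and at least 10 post-baseline diary days: "have at least 10 days of post baseline efficacy assessments on the primary endpoint. The FAS will be used for all efficacy analysis". Section 6.1 restates the scope: "The FAS will be used for all efficacy analyses". Neither makes an exception for responder endpoints.

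**Responder rule.** For the secondary 50% responder endpoint, Section 6.3.1.1 states: "If a patient is early discontinued from the study, he/she will be counted as a non-responder". Section 6.4.1.1 applies the same rule to the exploratory 12-week responder endpoints. Neither section sets a minimum number of diary days.

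**Role in the testing sequence.** The "proportion of patients reaching at least 50% reduction in the monthly average number of headache days of at least moderate severity" is tested at step 4 (675/225/225 mg versus placebo) and step 7 (675 mg/placebo/placebo versus placebo) in Section 4.4. After a step with p > 0.05, "no further comparisons will be interpreted inferentially". Section 6.3.2 names the stratified Cochran-Mantel-Haenszel test for this endpoint and no other population.

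**Origin of the 10-day rule.** The amendment history and Section 11 attribute the change from 1 assessment to 10 days to FDA review.

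**The concern.** A minimum number of diary days makes sense for a mean prorated to 28 days, because a handful of days gives an unstable value. It does nothing for a patient whose outcome is fixed by having discontinued. Under the SAP as written, a treated patient who leaves with 12 diary days is a non-responder, and one who leaves with 6 is not analysed.

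No other planned responder analysis brings these patients back. The per-protocol repeat requires study completion (Section 3.4), and the multiple imputation analysis covers the primary variable only (Section 6.2.3.2). The disposition table in Section 5.2 counts "patients in the safety population, ITT population, FAS and per-protocol analysis set", so the number lost per arm can be derived, but a count is not an analysis.

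The endpoint is confirmatory. Step 4 gates step 5, which is the 675 mg/placebo/placebo comparison on the primary variable, and everything after it. Removing certain non-responders after randomisation raises the responder rate of whichever arm loses more of them.

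**Working it through.** **Inputs from the SAP.** Section 2.3: 340 randomised per group, with "Assuming a 15% discontinuation rate, 340 patients per treatment group will be randomized". This reproduces: 289 / 0.85 = 340. Section 2.1: treatment period of 84 days. The SAP gives no responder rates and no count of patients with fewer than 10 diary days, so both are assumed below.

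**How many patients.** Planned discontinuations: 0.15 × 340 = 51 per arm. If they are spread evenly over 84 days with one diary entry per day, those leaving with at most 9 days number 51 × 9/84 = 5.5, or about 5 per arm (5.5/340 = 1.6%).

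**Effect on one arm.** Removing k certain non-responders from n multiplies the responder rate by n/(n − k). With n = 340, k = 3 adds 0.9% in relative terms and k = 10 adds 3.0%.

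**Effect on the difference.** Let eA and eP be the numbers excluded on active and placebo, and pA and pP the FAS responder rates. Restoring the excluded patients as non-responders gives

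all-treated difference = pA(340 − eA)/340 − pP(340 − eP)/340.

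The z values are from a pooled two-proportion test, an unstratified stand-in for the planned stratified test.

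| FAS rates (assumed) | Excluded, active / placebo | FAS difference | All-treated difference | z, FAS / all treated |
|---|---|---|---|---|
| 40% vs 20% | 5 / 5 | 20.0 | 19.7 | 5.65 / 5.63 |
| 40% vs 20% | 10 / 5 | 20.0 | 19.1 | 5.63 / 5.48 |
| 40% vs 20% | 5 / 10 | 20.0 | 20.0 | 5.62 / 5.72 |
| 30% vs 20% | 5 / 5 | 10.0 | 9.9 | 2.99 / 2.98 |
| 30% vs 20% | 10 / 5 | 10.0 | 9.4 | 2.98 / 2.86 |
| 30% vs 20% | 5 / 10 | 10.0 | 10.1 | 2.98 / 3.08 |

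Differences are in percentage points. The smallest z is 2.86, so no decision changes.

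**Borderline case.** Fix placebo at 112 responders among 340 treated and vary the active count.

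| Excluded, active / placebo | Active responders | p, FAS | p, all treated |
|---|---|---|---|
| 7 / 0 | 134 | 0.049 | 0.079 |
| 7 / 0 | 135 | 0.041 | 0.067 |
| 7 / 0 | 136 | 0.034 | 0.056 |
| 10 / 5 | 135 | 0.046 | 0.067 |
| 10 / 5 | 136 | 0.038 | 0.056 |
| 5 / 5 | none changes the decision | | |
| 5 / 10 | 137 | 0.064 | 0.047 |
| 5 / 10 | 138 | 0.054 | 0.039 |

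The window in which the denominator matters is 2 to 3 responders wide. It favours active or placebo depending on which arm loses more early dropouts.

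**How likely is the extreme split?** With 51 dropouts per arm, each with chance 9/84 of leaving that early, the probability of at least 7 exclusions on active is 0.303 and of none on placebo 0.0031. The product is about 0.001.

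**The case against.** A reader might infer that the SAP contradicts itself. It does not. Sections 3.3 and 6.1 say who is analysed; Sections 6.3.1.1 and 6.4.1.1 say how an analysed patient is classified. Inside the FAS the non-responder rule has a real job: it stops a dropout with, say, 20 good diary days from being scored a responder on prorated data. Nothing in the SAP says that treated patients outside the FAS belong in a responder denominator. This objection stands.

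The 10-day set is also deliberate and disclosed, and it followed regulatory review. That is a reason to leave it alone for the prorated continuous endpoints. It does not show that the responder denominator was considered, and the SAP does not say.

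The figure of about 5 per arm may be too high. Patients must meet "electronic headache diary compliance criteria during the 28-day run-in period" before randomisation, and no visit is scheduled between day 0 and day 28. Someone who leaves at the day 28 visit with ordinary compliance already has far more than 10 diary days. Only withdrawal in the first days after dosing, or near-total diary non-use, leads to exclusion. This also stands; the true number is unknown.

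Finally, moving to all treated patients brings in completers with fewer than 10 diary days, for whom the SAP gives no responder outcome. The change has to define one.

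**Conclusion.** Minor, and worth changing because it is cheap. The SAP makes a post-randomisation exclusion in a gatekeeping responder test that the endpoint's own non-responder rule makes unnecessary.

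The expected effect is very small and has no known direction. It rests on an assumed even spread of the planned 15% discontinuation and on assumed responder rates. In the cases worked, balanced exclusions of 5 per arm change no decision; a change needs both a borderline result and an imbalance between arms.

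A reader might go further and infer that steps 4 and 7 are biased towards active treatment, or that the 10-day set is wrong for the primary analysis. The SAP supports neither. Nothing in it suggests that very early dropout will differ by arm, and a diary minimum is reasonable for a prorated mean.

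**What to change.** Keep the FAS for the primary ANCOVA or rank test, the MMRM, the multiple imputation analysis and the other continuous endpoints.

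In Sections 3.3, 6.1, 6.3.1.1 and 6.4.1.1, state that the responder endpoints carrying the non-responder rule, including steps 4 and 7, are analysed on all randomised patients who received at least one dose. Count as non-responders:

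- every patient who discontinues early, whatever the number of diary days;
- any patient who completes with fewer than 10 diary days after the first dose.

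Every treated patient then has a defined outcome. The second item is a new rule and should be labelled as such.

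The cost is some SAP wording and one extra analysis-set flag. Responder rates may fall slightly, and the responder denominator will differ from that of the primary analysis, so table footnotes should say so.

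A separate clerical point, which does not support the claim above: the sentence in Section 6.3.2 on patients with fewer than 10 diary days refers to a missing-data method in Section 6.2.1, which contains none. Delete it or redirect it to Section 4.5.

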3.4. Per-Protocol Analysis Set

The per-protocol analysis set will consist of all patients who have completed the study without any violations of the inclusion/exclusion criteria or any violations or omissions of the drug administration. The efficacy analysis for the primary and secondary endpoints will be repeated for the per-protocol analysis set.

4. GENERAL ISSUES FOR DATA ANALYSIS

4.1. General

Descriptive statistics for continuous variables include count (n), mean, SD, standard error (SE), median, minimum, and maximum. Descriptive statistics for categorical variables include patient counts and percentages.

Summaries of potentially clinically significant abnormal values will include all post-baseline values (including scheduled, unscheduled, and early termination visits).

4.2. Specification of Baseline Values

Patients will complete electronic headache diary entries daily for 28-day run-in period and enter headache information (i.e., occurrence of headache, duration of headache, maximum severity of headache, and acute migraine-specific medication use) about the previous day into the electronic headache diary device.

If the run-in period is greater or less than 28 days, the baseline values for calculating the change from baseline of the monthly values of the efficacy variables will be normalized to 28 days. The baseline value for calculating change from baseline of the weekly values will be normalized to 7 days.

The efficacy baseline values during the 28-day run-in period derived from the e-diary include

- total headache days of at least moderate severity
- total number of migraine days
- total number of days of use of any acute headache medication
- total headache days of any severity
- total number of headache hours of at least moderate severity
- total number of headache hours of any severity
- total number of days of use of migraine-specific acute headache medications (triptans and ergot compounds) for the group of patients who use migraine-specific acute headache medications at baseline
- total number of days with nausea or vomiting
- total number of days with photophobia and phonophobia

Other efficacy baseline values that will be measured on day 0 before the 1st study drug administration include

- disability score, as measured by the HIT-6 ([Appendix C](#))
- quality of life, as measured by the MSQOL questionnaire ([Appendix D](#))
- health status, as measured by the EQ-5D-5L questionnaire ([Appendix F](#))
- patient depression status, as measured by the PHQ-2 and the PHQ-9 ([Appendix G](#))

- patient work productivity and activity impairment, as measured by the WPAI questionnaire ([Appendix H](#))

Other baseline values will be the last values prior to the 1st dose of study drug.

